### **Statistical Analysis Plan**

As of the writing and uploading of this plan, enrollment has not yet begun, and data have not yet been examined.

#### Primary Research Question: Do reminder emails increase scheduled WCC visits?

H1: Those who received reminder emails will have a higher percentage of WCC visits scheduled compared with those in the control group.

For all analyses, a logistic regression model will analyze the outcomes as a function of condition. The control condition will be the reference group. For all tests, two-tailed p-values < 0.05 will be used to determine statistical significance. Only the first WCC visits of patients within the study period will be analyzed.

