### **Background**

Regular attendance at recommended WCC visits is associated with having up-to-date immunizations. Standard care involves scheduling a follow-up WCC visit at the end of the current visit. However, if the child's parents do not choose to schedule a follow-up visit at that time or miss a WCC visit, they may not be offered another easy opportunity to schedule one. That is, they would have to remember to schedule a visit and contact the clinic proactively.

In this study, 30 days before a child is due for their WCC visit, parents who have not yet scheduled a WCC visit for up to 30 days (for 5-month-olds) or 60 days (for all other ages) after their child is due for a visit will be randomly assigned to two groups with a random number generator. One group will receive an email reminder, while the other group will not receive any reminder.

The randomization of participants to different conditions will be in place until 800 participants have been identified and randomly assigned to one of the arms (estimated sample to detect at least a 10% absolute difference) or 180 days, whichever comes first. To account for delays in updating clinical databases, the final outcome data will be checked 90 days after the last eligible visit (for a maximum study period of 270 days).

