#### Experimental conditions

A list of eligible participants will be generated each day, and a randomizing function in SQL will assign them to the treatment or control condition. Those in the treatment condition will be sent a reminder email, that tells the parent that their child will be due for a WCC in four weeks,

emphasize the importance of these visits, and provide contact information for them to schedule an appointment, as well as a convenient hyperlink for those with online patient portal access. Those in the control condition will not be sent a reminder email.

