#### Outcome measures

The primary outcome measure will be a binary variable indicating whether a WCC visit was scheduled 30–60 days from the email, as determined by billing code; in the absence of a billing code, either a visit type or reason that mentions WCC will be included.

The secondary outcome measures will be a binary variable indicating whether a WCC visit was completed 30–60days from the email (as established by billing codes) and a binary variable indicating whether the child's immunization status is up to date 60 days from the email (as established by the absence of immunization care gaps in the record).

Additional data that will be collected will include email opens, scheduling follow-up WCC visits (i.e., 61–150 days after the email), having any General Pediatrics visit 30–60 days from the email, having any office visit 30–60 days from the email, and immunization status for Measles/Mumps/Rubella vaccine (MMR), Hepatitis A, Hepatitis B, and Varicella.

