# Secondary Research Question: Do reminder emails increase completed WCC visits and immunization?

H2: Those who received reminder emails will have a higher percentage of WCC visits completed compared with those in the control group.

H3: Those who received reminder emails will have a higher percentage of eligible children with up-to-date immunizations compared with those in the control group.

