#### **Additional Analyses**

For the primary and secondary analyses, we will conduct separate robustness checks adding immunization status at the day the email was sent as a control variable.

To examine engagement with the email, the percentage of people who opened emails will also be examined.

We will also examine the broader effects of the intervention on engagement with the health system, specifically, General Pediatrics visits and any office visits.

A more distal goal of the project is to get otherwise unengaged parents to continue scheduling WCC visits for their child. Thus, we will also look at the effect of the intervention on WCC visits for the child's next due date.

Finally, immunization for MMR, Hepatitis A, Hepatitis B, and Varicella are of particular interest for the research team, so we will also examine if the intervention individually affected each of those immunization rates.

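### The main H3 test leaves out the child's immunization status at day 0, which the plan collects but uses only in a robustness check

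*Combined protocol and SAP*

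**What the plan says.** The SAP sets one model under its Primary Research Question heading and applies it to all analyses: "a logistic regression model will analyze the outcomes as a function of condition". Control is the reference group, and "two-tailed p-values < 0.05 will be used to determine statistical significance". No covariate is named.

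That model therefore also tests the third hypothesis: "H3: Those who received reminder emails will have a higher percentage of eligible children with up-to-date immunizations". The Outcome measures section defines this endpoint as whether the child's "immunization status is up to date 60 days from the email", judged by there being no open immunization care gap in the record.

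Under Additional Analyses, the SAP plans for the primary and secondary outcomes "separate robustness checks adding immunization status at the day the email was sent as a control variable". Nothing in the plan makes that adjusted model the main test for H3.

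On timing, the Experimental conditions section states: "Those in the control condition will not be sent a reminder email". So the date attached to the covariate has no literal meaning for half of the trial.

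**The concern.** For H1 and H2, immunization status at day 0 is an ordinary covariate. For H3 it is the baseline measurement of the outcome itself, and in most before-and-after measurements that is the best single predictor available. A main test that ignores it leaves explainable variation in the residual.

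The sponsor already collects the variable and already plans the adjusted model, so the only open question is which of two prespecified models carries the H3 conclusion. As written, the less powerful one does. If the two disagree, the plan's answer is the one from the model that uses less of the data.

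A smaller point sits in the same clause. The covariate needs a reference date that exists in both arms, and the plan gives one only for families who are emailed.

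**Working it through.** **Inputs from the documents.** Up to 800 participants, two arms, two-sided α = 0.05, and a sample size described as the "estimated sample to detect at least a 10% absolute difference". No outcome, control rate, power or allocation ratio is attached to that figure.

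**Assumptions.** 1:1 allocation with all 800 reached (400 per arm); 50% up to date at day 0; H3 rates of 45% versus 55%, which is the plan's 10-point difference centred on 50%; correlation r between day-0 and day-60 status from 0 to 0.7.

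**Step 1: reproduce the plan's sample size.** With pooled variance and an assumed power of 80%:

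n per arm = [1.96·√(2·0.50·0.50) + 0.8416·√(0.45·0.55 + 0.55·0.45)]² / 0.10² = (1.3859 + 0.5921)² / 0.01 ≈ 391.3, so 392 per arm and 784 in total.

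This is within 3% of 800, so 10 points around a 50% rate is a reasonable reading. It is not the only one: 90% power with 20% versus 30% also gives 784.

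**Step 2: unadjusted H3 power with 400 per arm.**

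z = (0.10 − 1.96·√(0.50/400)) / √(0.495/400) = (0.10 − 0.0693) / 0.0352 ≈ 0.873, so power is 80.9%.

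**Step 3: effect of adjusting.** Adjusting for a baseline value with correlation r multiplies the variance of the risk difference by about 1 − r². This is equivalent to 400/(1 − r²) per arm:

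- r = 0.3: 800/0.91 ≈ 879 participants' worth of information.
- r = 0.5: 800/0.75 ≈ 1,067 participants' worth.

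The formula was checked by simulation, with 40,000 trials per setting. It compared the condition-only logistic model with condition plus day-0 status, using the standardised risk difference with influence-function variance.

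| r | Power, formula | Power, simulated | Variance ratio (risk difference) | 95% CI width, points | SE of log OR | Verdicts differ |
|---|---|---|---|---|---|---|
| 0 | 80.9% | 81.0% | 1.00 | 13.8 | 0.143 | 0.5% |
| 0.1 | 81.3% | 81.5% | 0.99 | 13.7 | 0.143 | 2.1% |
| 0.2 | 82.4% | 82.7% | 0.96 | 13.5 (13.8·√0.96) | 0.146 | 4.3% |
| 0.3 | 84.4% | 84.6% | 0.90 | 13.1 | 0.150 | 6.7% |
| 0.5 | 90.5% | 90.5% | 0.75 | 11.9 | 0.166 | 12.0% |
| 0.7 | 97.8% | 97.8% | 0.51 | 9.8 | 0.209 | 16.8% |

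For comparison, the unadjusted model had simulated power of 81.0–81.6% in every setting, a CI width of 13.8 points and a log odds ratio SE of 0.142. Type I error was 5.1–5.3% unadjusted and 5.0–5.2% adjusted, so both tests hold their level.

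**Step 4: why power rises although the SE of the log odds ratio also rises.** The adjusted odds ratio is conditional and lies further from 1. At r = 0.5 it is about 1.72, against 1.49 unadjusted. The test statistics are ln(1.49)/0.142 ≈ 2.81 and ln(1.72)/0.166 ≈ 3.27. Their ratio, 1.16, agrees with 1/√0.75 = 1.155. The gain in interval width therefore shows on the risk-difference scale and not on the odds-ratio scale.

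**Step 5: sensitivity to the assumptions.**

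- 60% versus 70% with 60% up to date at day 0: 84.5% unadjusted; 84.8%, 87.8% and 93.1% adjusted at r = 0.1, 0.3 and 0.5.
- 50% versus 60% with 50% or 70% up to date at day 0 (separate simulation, 10,000 trials per setting): at r = 0.5, 81% unadjusted against 90–91% adjusted.
- A 5-point difference, 47.5% versus 52.5% (formula): 29.4% unadjusted; 29.6%, 31.7% and 37.3% adjusted at r = 0.1, 0.3 and 0.5.

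**The case against.** The strongest reply is that nothing is missing. The adjusted H3 result will be produced under the current plan, the unadjusted comparison of randomized arms is valid, and one model for all three hypotheses is simple. All of that is true, and it limits the point to which model is the main one.

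The size of the gain is also open. Every child is due for a well-child visit about 30 days after list generation, between the two measurements. A child up to date at day 0 may have a new dose fall due and show a care gap at day 60. That could pull r down, and at r = 0.1 the gain is about half a power point. Nothing in the documents supports r of 0.5 or more. The 10-point effect may also be generous for immunization, which moves only if the email leads to a visit and the visit to vaccination. With 5 points H3 is underpowered under either model. These objections stand as limits on the benefit. They do not favour the unadjusted model, because adjusting costs essentially nothing at r = 0.

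Two narrower objections are also fair. Disagreement between two valid tests is not an error rate. And the missing control-arm date affects the outcome windows as well as this covariate, although list date is the natural reading.

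Finally, the statement that "enrollment has not yet begun" describes the day the plan was written. If outcome data have since been seen, changing the main model would be post hoc.

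**Conclusion.** The concern holds, as a matter of efficiency on a secondary outcome. The condition-only H3 test keeps its 5% error rate, and the H1 decision is untouched.

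Under the 10-point assumption with 400 per arm, adjustment is worth about half a power point at r = 0.1, about 3 to 4 points at r = 0.3 and about 9 at r = 0.5. The confidence interval for the risk difference narrows from 13.8 points to 13.7, 13.1 and 11.9 respectively. The correlation, the H3 rates, the H3 effect and the allocation ratio are all assumed, so the direction is firm and the size is not. The change is worth making because it can help, costs almost nothing if it does not, and uses data already in the plan.

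No comparable gain is claimed for H1 or H2. If r there is about 0.1 or less, the variance reduction is at most about 1% (0.1² = 0.01).

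**What to change.** For H3 only, amend the SAP as follows:

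- **Main model:** logistic regression of day-60 up-to-date status on condition and day-0 up-to-date status, both by the care-gap definition in Outcome measures. The H3 conclusion rests on this model.
- **Day 0:** the date of list generation, by the same rule in both arms.
- **Estimate:** the standardised (marginal) risk difference with its 95% CI, since H3 is stated as a percentage, with the variance method named (for example influence-function or bootstrap).
- **Supportive analysis:** the condition-only model now specified.

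H1 and H2 can stay as planned.

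The cost is a few sentences of SAP text, with no new data and no change in sample size. There are two small drawbacks. The adjusted odds ratio is conditional and will not match the unadjusted one, and the standardisation step has to be specified and programmed. The amendment should be dated before any outcome data are examined; if that is no longer possible, the present main model should stand.

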#### Methods

#### Sample

The eligible participants will be parents (or the contact of record) of children aged 5, 8, 11, 14, or 17 months at the time of list generation. The child will need to have no WCC visits scheduled 30 days (for 5-month-olds) or 60 days (for all other ages) after their due date for a WCC (i.e., month 6, 9, 12, 15, or 18) and be currently seen at Pediatric clinics within Geisinger's umbrella (i.e., have at least one prior visit). In addition, the parent will need to have an email address and not have opted out of receiving any system emails.

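### The main model for H1–H3 leaves out age cohort, a baseline variable held for every child; prespecifying it is a free but modest efficiency gain, and only if age predicts the outcome

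*Combined protocol and SAP*

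**What the plan says.** - **Model.** Under Primary Research Question, one specification covers all analyses: "a logistic regression model will analyze the outcomes as a function of condition". Control is the reference group and "two-tailed p-values < 0.05 will be used to determine statistical significance". No other term is named for H1, H2 or H3.
- **Who enters.** Under Sample, eligibility is limited to parents of "children aged 5, 8, 11, 14, or 17 months at the time of list generation". The look-ahead rule depends on age: the child must have "no WCC visits scheduled 30 days (for 5-month-olds) or 60 days (for all other ages) after their due date".
- **Assignment.** Under Background, families are "randomly assigned to two groups with a random number generator". Under Experimental conditions, "a randomizing function in SQL will assign them to the treatment or control condition". Neither section mentions stratification by age.
- **Other covariates.** Additional Analyses adds one covariate, immunization status on the day of the email, as a robustness check on the primary and secondary outcomes. Age cohort is not in that check either.
- **Size.** Under Background, 800 is the "estimated sample to detect at least a 10% absolute difference". Power, control rate and rates by age are not stated.

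**The concern.** The trial pools five cohorts that are due for five different visits and are screened under two look-ahead rules. A 5-month-old already booked 31–60 days after the due date can enter; an older child with the same booking cannot. Booking, attendance and immunization rates could therefore differ by age. The cohort is fixed before assignment and, because it is needed to build the daily list, should have no missing values. Adjusting for such a variable normally gives a somewhat sharper comparison from the same children, and the plan does not use it.

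What is at stake is a little power. That matters most if control rates are near 45–50%, where 800 children leave little reserve, or if the 180-day limit stops enrolment below 800. Timing matters too: the plan says enrolment has not begun and no data have been examined, so adjustment can be prespecified now, whereas adjustment chosen after seeing data would be open to challenge.

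**Working it through.** **Inputs from the documents:** total N = 800, absolute difference 10 points, two-sided alpha 0.05, five age cohorts.

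**Assumptions (not in the documents):** 1:1 allocation (400 per arm), equal cohorts (80 per arm each), control rates evenly spaced across cohorts around a mean of 20%, 30%, 45% or 50%, and a common odds ratio within cohorts chosen to give a 10-point difference overall. Spread means the gap between the lowest and highest cohort control rates.

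**1. The plan's 800.** It cannot be reproduced from stated inputs alone, because power and control rate are missing. With 80% power and 45% v 55%:

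n per arm = [1.96·√(2·0.5·0.5) + 0.8416·√(0.45·0.55 + 0.55·0.45)]² / 0.10² = (1.386 + 0.592)² / 0.01 = 391.3, so 392 per arm and 784 in total.

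40% v 50% and 50% v 60% each give 776. At 90% power, 20% v 30% gives 784. So 800 is consistent with standard choices.

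**2. Condition-only power at 45% v 55%.**
- Log odds ratio = ln(0.55/0.45) − ln(0.45/0.55) = 0.401.
- SE = √[1/(400·0.2475) + 1/(400·0.2475)] = 0.1421.
- Power = Φ(0.401/0.1421 − 1.96) = 80.6%.

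**3. Power with age cohort in the model.** The SE of the conditional log odds ratio is 1/√Σ[80·v0·v1/(v0+v1)], summed over cohorts, with v = p(1−p) in each arm. At a 45% control rate and a 30-point spread the log odds ratio moves from 0.401 to 0.421 and the SE from 0.1421 to 0.1456, giving power of 82.3% (unrounded inputs). The SE rises; power improves because the conditional effect lies further from zero.

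**4. Variance of the age-standardised difference.** Per-arm variance × 400:
- unadjusted: P0(1−P0) + P1(1−P1);
- adjusted: mean over cohorts of (v0 + v1), plus half the between-cohort variance of the difference.

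At 45% and a 20-point spread: 0.2425 + 0.2425 + 0.000001 = 0.4850 against 0.4950, a ratio of 0.980. Equivalent extra participants = 800/0.980 − 800 ≈ 16.

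| Mean control rate | Spread (points) | Power, condition only | Power, with age | Fall in variance of standardised difference | Equivalent extra participants |
|---|---|---|---|---|---|
| 20% | 10 | 90.1% | 90.4% | 0.9% | 7 |
| 20% | 20 | 90.1% | 91.1% | 3.7% | 30 |
| 20% | 30 | 90.1% | 92.4% | 8.4% | 73 |
| 30% | 10 | 84.1% | 84.3% | 0.6% | 5 |
| 30% | 20 | 84.1% | 85.0% | 2.6% | 21 |
| 30% | 30 | 84.1% | 86.1% | 5.8% | 49 |
| 30% | 40 | 84.1% | 87.7% | 10.4% | 93 |
| 45% | 10 | 80.6% | 80.8% | 0.5% | 4 |
| 45% | 20 | 80.6% | 81.4% | 2.0% | 16 |
| 45% | 30 | 80.6% | 82.3% | 4.6% | 38 |
| 45% | 40 | 80.6% | 83.7% | 8.1% | 71 |
| 50% | 20 | 81.0% | 81.7% | 2.0% | 16 |
| 50% | 40 | 81.0% | 84.0% | 7.8% | 68 |

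With no spread the two powers are equal. A 40-point spread around 20% would put one cohort at zero, so it is not shown. A Wald test on the standardised difference gains much the same: at 45% and a 40-point spread, 81.1% to 84.3%.

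**5. Simulation check** (4,000 trials per scenario, 30-point spread): 81.0% to 82.6% at 45%, and 90.2% to 92.9% at 20%. Type I error was 4.4–5.4% across scenarios, with and without adjustment.

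**6. If enrolment stops early.** At 600 children, a 50% control rate and a 40-point spread, power goes from 69.1% to 72.5%.

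**The case against.** The strongest reply is that nothing here is wrong. Under randomization the condition-only test is valid, and an unadjusted primary analysis with an adjusted robustness check is a legitimate design. That stands.

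It is also fair that the documents give no rate by age. The 30/60-day rule governs who enters, while the primary outcome window is the same for every cohort. The rule makes an age difference plausible but does not show one. At spreads of 20 points or less the gain is about 1 power point at most. That stands too, and it limits the claim.

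Three stronger readings are tempting and not supported:
- **A large loss.** With control rates running from 20% to 80% across cohorts, power would go from about 81% to about 88%. Nothing in the documents suggests a 60-point spread, least of all among families all selected for having no visit booked in the look-ahead period.
- **Residual noise, as in a linear model.** This does not carry over to a logistic coefficient, whose SE rises on adjustment (step 3). The variance reduction is real on the standardised difference.
- **Chance age imbalance as a second problem.** For a cohort holding 20% of the sample, the SD of the between-arm difference in its share is √(2·0.2·0.8/400) = 2.8 points. At a 20-point spread, imbalance across cohorts moves the risk difference by an SD of only about 0.5 point, against an SE of about 3.5. The unadjusted SE already contains this, so it is the same loss seen from another side.

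What survives is that the variable is held at no cost, no scenario showed a material loss from using it, and it can be prespecified only before data are seen.

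**Conclusion.** The point holds as a modest, free improvement. The plan is not in error, and a reader should not infer that the condition-only result would be biased or its p-value wrong.

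If age predicts the outcome, adjustment at 800 children and a 10-point effect adds about 0 to 1 power point for spreads up to 20 points, and about 2 to 4 points for spreads of 30–40. The variance of the age-standardised difference falls by about 2–4% at 20 points and 8–10% at 40, equivalent to roughly 16–30 and 68–93 extra participants. If age does not predict the outcome, the gain is zero.

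These figures rest on 1:1 allocation, equal cohorts, mean control rates of 20–50% and a common odds ratio, none of which the documents state. They assume a 10-point effect; H2 and H3 were not computed separately, though the reasoning is the same.

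**What to change.** Before enrolment, amend the model sentence under Primary Research Question along these lines: *For H1, H2 and H3 the main analysis is a logistic regression on condition and age cohort (five-level factor: 5, 8, 11, 14, 17 months). Inference is based on the age-standardised difference in percentages between arms, with its 95% CI. The condition-only model is a supporting analysis.*

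The same sentence should name the standard-error method for the standardised difference (delta method or bootstrap) and say which model the planned immunization-status check is added to. Reporting a difference in percentages keeps the effect marginal and matches the way H1–H3 are worded.

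The cost is one or two sentences and four extra parameters in a model on 800 children. No new data are needed, and neither randomization nor sample size changes.

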# Secondary Research Question: Do reminder emails increase completed WCC visits and immunization?

H2: Those who received reminder emails will have a higher percentage of WCC visits completed compared with those in the control group.

H3: Those who received reminder emails will have a higher percentage of eligible children with up-to-date immunizations compared with those in the control group.

#### **Additional Analyses**

For the primary and secondary analyses, we will conduct separate robustness checks adding immunization status at the day the email was sent as a control variable.

To examine engagement with the email, the percentage of people who opened emails will also be examined.

We will also examine the broader effects of the intervention on engagement with the health system, specifically, General Pediatrics visits and any office visits.

A more distal goal of the project is to get otherwise unengaged parents to continue scheduling WCC visits for their child. Thus, we will also look at the effect of the intervention on WCC visits for the child's next due date.

Finally, immunization for MMR, Hepatitis A, Hepatitis B, and Varicella are of particular interest for the research team, so we will also examine if the intervention individually affected each of those immunization rates.

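### The two broader-engagement outcomes do not exclude WCC visits, so an email effect confined to WCC visits would carry into them in diluted form and could be read as broader engagement

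*Combined protocol and SAP*

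**What the plan says.** The SAP, under Additional Analyses, announces: "We will also examine the broader effects of the intervention on engagement with the health system, specifically, General Pediatrics visits and any office visits".

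The protocol's Outcome measures section lists the matching variables among the additional data: "having any General Pediatrics visit 30–60 days from the email, having any office visit 30–60 days from the email". The same section defines one secondary outcome as "a binary variable indicating whether a WCC visit was completed 30–60days from the email (as established by billing codes", so all three share one window. Neither any-visit variable carries an exclusion for WCC visits, and no non-WCC version is planned anywhere.

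On setting, the Sample section requires the child to "be currently seen at Pediatric clinics within Geisinger's umbrella (i.e., have at least one prior visit". On analysis, the SAP says "For all analyses, a logistic regression model will analyze the outcomes as a function of condition", and "For all tests, two-tailed p-values < 0.05 will be used to determine statistical significance".

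**The concern.** The email asks the parent to book a WCC visit. H1 and H2 already test whether that visit is scheduled and completed. An analysis presented as showing broader effects invites the reader to look for something more than that visit.

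As worded, a completed WCC would ordinarily satisfy the office-visit outcome, and would satisfy the General Pediatrics outcome if it is recorded under that department. If the email raised WCC completion and changed no other care, both outcomes would still tend to shift upwards. Each outcome is modelled on condition alone, so the any-visit result does not show how much of a shift is the WCC visit itself. The 0.05 threshold covers all tests, so a significant result could be reported as broader engagement when only the requested visit had changed.

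**Working it through.** **Inputs from the documents.** Total sample 800, or fewer if 180 days pass first; a 10-percentage-point absolute difference as the target (Background); two-sided 0.05 (SAP, Primary Research Question); the same 30–60 day window for completed WCC and both any-visit outcomes (Outcome measures).

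**Assumptions, not in the documents.** 1:1 allocation with the full 800, so 400 per arm; the completed-WCC rates w; a non-WCC visit rate q that is equal in both arms and independent of WCC, so that the true effect on other visits is zero; and every completed WCC counting towards the any-visit outcome.

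**The plan's own figure.** The 800 cannot be derived from the plan, because it gives neither the power nor the control rate. It is consistent with 80% power and a control rate near 50%: 45% versus 55% requires 784 in total. Nothing below disputes it.

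**Formula.** A child has any visit unless both kinds are absent:

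P(any) = 1 − (1 − w)(1 − q)

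With the same q in both arms, the difference in any-visit rates is (w_email − w_control) × (1 − q). The WCC effect carries through, shrunk by the share of children who have another visit anyway.

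**Worked case, w = 40% control and 50% email, q = 20%.**
- Control: 1 − 0.60 × 0.80 = 0.52
- Email: 1 − 0.50 × 0.80 = 0.60
- z = 0.08 / √(0.52 × 0.48/400 + 0.60 × 0.40/400) = 2.29, p = 0.022

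**The same calculation over a range of q.** The p-value is the one obtained if the observed rates equal the expected ones.

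| q | Control | Email | Difference | p |
|---|---|---|---|---|
| 10% | 46% | 55% | 9 points | 0.011 |
| 20% | 52% | 60% | 8 points | 0.022 |
| 30% | 58% | 65% | 7 points | 0.041 |
| 40% | 64% | 70% | 6 points | 0.071 |

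**Chance of p < 0.05 with no change in other visits.** For w rising from 30% to 40% with 400 per arm: 84% at q = 0, 73% at q = 10%, 62% at 20%, 51% at 30% and 33% at 50%. Across starting rates of 20%, 30% and 45%, each rising 10 points, and q from 0 to 50%, the chance runs from about 91% down to 31%. For an outcome restricted to non-WCC visits it would be the nominal 5%.

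**If WCC visits replace other visits.** Let w rise from 30% to 40% while q falls from 20% to 15%:
- Control: 1 − 0.70 × 0.80 = 0.44
- Email: 1 − 0.60 × 0.85 = 0.49

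The difference shrinks to 5 points, with about a 29% chance of significance. A smaller any-visit effect can therefore come from a higher q or from substitution, and the any-visit rate alone does not say which.

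**The case against.** The strongest reply is that any contact with the health system is a legitimate measure in its own right. *Broader* can mean a wider outcome, namely whether the child was seen at all, and the next paragraph of Additional Analyses is concerned with parents who are otherwise unengaged. On that reading the inclusion of WCC visits is intended. This stands: the any-visit outcomes are not errors and should stay. What remains open is which conclusion they can carry.

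The overlap is also inferred, not stated. It rests on the word *any*, the shared window and the absence of an exclusion. The inference is strongest for office visits. For General Pediatrics it also needs WCC visits to be recorded under that department. The Sample section makes that plausible but does not establish it. A reader might infer that every child who meets H2 necessarily meets both outcomes; the documents do not go that far.

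A reader might also infer that the planned outcomes cannot distinguish the WCC visit from other care at all. That is too strong. If completed WCC is a subset of any visit, subtraction gives the share of children with only non-WCC visits. In the worked case this is 52 − 40 = 12% in control and 60 − 50 = 10% in the email arm, which does not suggest broadening. The subtraction misses children who had both kinds of visit, however. From these marginal rates alone, the non-WCC rate could lie anywhere from 12% to 52% in control and from 10% to 60% in the email arm. Planned outcomes read together help, but do not replace a direct count.

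Finally, these are additional analyses without a numbered hypothesis. That is correct and limits the weight of the point.

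**Conclusion.** The point holds as a modest one. On the plain wording, an email effect confined to completed WCC visits would show up in the any-office-visit outcome, and in the General Pediatrics outcome to the extent that WCC visits are recorded there. Under the assumed rates, a 10-point WCC effect appears as about 6 to 9 points for non-WCC rates of 40% to 10%.

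It would be wrong to conclude that a positive H2 makes both outcomes significant. At a non-WCC rate of 40% the illustrative p-value is 0.071, and the chance of significance falls to about a third or less in parts of the range examined. The sizes rest on an assumed full 10-point gain in completed WCC visits, independence, unchanged other visits and 400 per arm. The upward direction needs less: that completed WCC visits rise, that at least some of the added visits go to children with no other visit in the window, and that other visits do not fall enough to cancel the gain.

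Only the interpretation of additional analyses is affected. The conclusions for H1, H2 and H3 do not change.

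**What to change.** Keep both any-visit outcomes and describe them as total engagement. In Outcome measures and Additional Analyses, add two companion outcomes over the same 30–60 days: any General Pediatrics visit other than a WCC, and any office visit other than a WCC.

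Identify the WCC visits to be excluded as the completed-WCC secondary outcome does, by billing codes. The fallback on visit type or reason belongs to the scheduled-WCC outcome. Used as the main rule here, it would leave a completed visit with a WCC reason but no WCC billing code outside both the completed-WCC and the non-WCC outcomes. Use it instead as a sensitivity check that also excludes completed visits whose type or reason mentions WCC.

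Report any-visit, completed-WCC and non-WCC results side by side by arm. Claim an effect beyond the WCC visit only if the non-WCC outcome supports it. Do not read a fall in non-WCC visits by itself as reduced engagement, because a WCC visit may replace another visit.

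The cost is a few lines of SAP text, one extra filter on data already being collected, and two more exploratory tests. Power for non-WCC visits may be low. The SAP states that enrollment has not begun and no data have been examined, so on that footing the change can be made before any result is known.
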